**STUDY SUMMARY**

Title	Phase II trial of Ceritinib in combination with Stereotactic Ablative Radiation in ALK -rearranged metastatic lung adenocarcinoma
Short Title	Ceritinib and SABR in ALK + lung adenocarcinoma
Protocol Number	XXX
Phase	II
Methodology	Open label, Dual arm
Study Duration	Three years
Study Center(s)	single center
Objectives	Prolongation of progression free survival in lung adenocarcinoma with targeted therapy and radiation
Number of Subjects	33
Diagnosis and Main Inclusion Criteria	Metastatic/locally advanced lung adenocarcinoma harboring a ALK rearrangement
Study Product(s), Dose, Route, Regimen	Ceritinib (LDK378) 450 mg PO daily
Duration of administration	Until progression/intolerance of therapy. Projected 14 months for patients who progressed on crizotinib therapy and 20 months for those who have not been treated previously with an ALK inhibitor.
Reference therapy	Published progression free survival with ceritinib (LDK378) alone
Statistical Methodology	Sample size calculated on the basis of prolongation of progression free survival of patients treated on this protocol compared to published survival data. Kaplan Meier Methods will be used to estimate progression-free survival and overall survival

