#### 1.1.2 Treatment for *ALK*+ lung adenocarcinoma

Patients with lung adenocarcinoma now routinely have molecular/genetic testing performed on their tumor. Approximately 2-8% of patients with lung adenocarcinoma demonstrate a rearrangement in the anaplastic lymphoma kinase (*ALK*) gene [3, 4]. Due to the large number of lung cancer cases annually, this small percentage represents thousands of patients every year in the US.

*ALK* was identified as a chromosome translocation-produced protein in anaplastic large cell lymphomas (ALCL). In lung cancer, a fusion was identified between *ALK* and the echinoderm microtubule-associated protein like 4 (*EML4-ALK*) [3].

Patients with *ALK* rearrangements tend to be younger with less smoking history. The exact cause of the rearrangement is unclear. *ALK* rearrangements are rarely found in squamous cell cancer.

Crizotinib has been tested as an oral *ALK*-inhibitor. This compound has dramatically transformed treatment for *ALK* positive lung cancer. Crizotinib resulted in clinical response rates in more than 50% of 255 patients treated [5]. The median duration of response was 9-11 months. Crizotinib is FDA approved for the treatment of *ALK* positive lung cancer.

The NCCN guidelines recommend *ALK* inhibitor therapy be the first treatment for patients with *ALK* positive lung cancer [6]. However, the response to crizotinib is not durable, with many patients demonstrating progression within one year of treatment initiation. The central nervous system is a common site of progression [7].

Ceritinib is a second generation *ALK* inhibitor with 20 times greater potency. 246 patients were treated with ceritinib in a phase I trial [8]. 163 had previously been treated with an *ALK* inhibitor and 83 were *ALK*-inhibitor naïve. The overall response rate was 58%, with median duration of response being 10 months for those not previously treated with an *ALK* inhibitor, and 6.9 months for those previously treated

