## 9.2 Sample Size and Accrual

The results of a Phase I trial of ceritinib in *ALK*-rearranged metastatic adenocarcinoma were reported recently (Shaw et al., 2014). Ceritinib demonstrated activity in patients with an overall response rate of 57% at doses of 400 mg or greater. The PFS reported was 7 months for those with prior crizotinib treatment and 10 months for those who had not received any crizotinib. Toxicities and adverse events were also reported. This study offers contemporary, relevant historical control data for comparison purposes.

The sample size calculation is based on the primary endpoint, progression-free survival, and the assumption that patients are randomized until the end of accrual. The sample size is calculated separately for each cohort.

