## 9.3 Data Analyses Plans

We will use Kaplan-Meier methods to estimate the progression-free survival, time to 2nd and 3rd SABR and overall survival.

Duration of response (defined in 6.1.5) duration will be summarized for patients who responded. Descriptive summary statistics like median, 25% and 75% percentiles will be used.

Toxicities are dichotomized as none versus any, or none and mild versus moderate to severe.

The rates of overall response, toxicity and adverse events as well as their 95% confidence intervals will be estimated using exact binomial method.

We will compare the rates of toxicity and adverse events in this study with those of historical controls by the Fisher's exact test.

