##### **9.10.2.2 Adverse events (AEs)**

Summary tables for adverse events (AEs) will include only AEs that started or worsened during the on-treatment period, the treatment-emergent AEs. However, all safety data (including those from the pre and post-treatment periods) will be listed and those collected during the pre-treatment and post-treatment period are to be flagged.

The incidence of treatment-emergent adverse events (new or worsening from baseline) will be summarized by system organ class and or preferred term, severity (based on CTCAE grades), type of adverse event, relation to study treatment by

Deaths reportable as SAEs and non-fatal serious adverse events will be listed by patient and tabulated by type of adverse event and.

Specific safety event categories (SEC) will be considered. Such categories consist of one or more well-defined safety events which are similar in nature and for which there is a specific clinical interest in connection with the study treatment(s).

For each specified category, number and percentage of patients with at least one event per category will be summarized.

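### The Fisher test of crude toxicity proportions against published ceritinib rates is confounded by time on drug and by dose, with an uncertain net direction

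*Combined protocol and SAP*

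**What the plan says.** Section 9.3 (Data Analyses Plans) defines the quantities: "The rates of overall response, toxicity and adverse events as well as their 95% confidence intervals will be estimated using exact binomial method". So a rate here is a share of patients. The cut-points are given as "Toxicities are dichotomized as none versus any, or none and mild versus moderate to severe". The comparison follows: "We will compare the rates of toxicity and adverse events in this study with those of historical controls by the Fisher's exact test". No significance level, sidedness or control dataset is given for it in that section.

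Section 9.2 describes the Phase I ceritinib trial, notes that its toxicities were reported, and adds: "This study offers contemporary, relevant historical control data for comparison purposes". The endpoint table in section 9.1 also sets toxicity against historical controls, and section 2.0 (Cohort A) hypothesises that the combination is as safe as published experience.

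The counting window is in section 9.10.2.2: "Summary tables for adverse events (AEs) will include only AEs that started or worsened during the on-treatment period". Section 9.10 summarises duration of ceritinib exposure but does not link it to the comparison.

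On duration, the Study Summary says: "Projected 14 months for patients who progressed on crizotinib therapy and 20 months for those who have not been treated previously" with an ALK inhibitor. Section 9.2 says of the Phase I trial: "The PFS reported was 7 months for those with prior crizotinib treatment and 10 months for those who had not received any crizotinib". Sections 2.2.1, 5.2.2 and 6.1.6 let ceritinib continue after some progression events. On dose, Table 4-1 and section 4.1.1.1 give 450 mg with food; section 7.1.4 says the Phase I expansion ran at 750 mg.

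**The concern.** The share of patients who ever have an event depends on how long they are watched on drug and on the dose they take. Fisher's exact test on ever/never counts cannot separate either of these from an effect of SABR.

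If SABR prolongs time on ceritinib, as the trial hopes, patients accumulate more ceritinib events at an unchanged monthly risk, and the combination can look more toxic. If the dose used here produces fewer events per month, the comparison can look reassuring even when SABR adds harm. In addition, at least the first 10 weeks of each patient's on-treatment period precede SABR, so part of the numerator cannot bear on SABR at all.

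At stake is the reading of the stated safety objective: a significant or a non-significant p-value could each be taken as an answer that the comparison does not contain.

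**Working it through.** **The plan's own figures.** There is no stated power, alpha or sample size for the Fisher comparison, so nothing can be reproduced for it. The factor of 2 in duration is the PFS design alternative: 20/10 = 14/7 = 2. The cohort sizes built on it reproduce closely. The one-sample exponential log-hazard formula is n = [1.645/√p0 + 0.842/√p1]² / (ln 2)², with p0 and p1 the event probabilities under null and alternative (36 months accrual, 12 months follow-up).
- Cohort A: p0 = 0.840, p1 = 0.623, n = 17.04, rounded up to 18 (stated 18).
- Cohort B: p0 = 0.917, p1 = 0.742, n = 15.11, rounded up to 16 (stated 15).

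**Plausible exposure ratios.** For exponential time on drug, mean observed time = event probability × median / ln 2.
- Followed to discontinuation, as section 2.3 implies, with the hoped-for PFS: ratio 2.
- Cut at 48 months, Cohort A: 0.623 × 28.85 = 18.0 months under the alternative and 0.840 × 14.43 = 12.1 under the null, ratio 1.48. Against the uncut historical mean of 14.43, ratio 1.25.
- Cut at 48 months, Cohort B: 15.0 and 9.3 months, ratio 1.62. Against the uncut 10.10, ratio 1.48.
- No effect of SABR on PFS: near 1, apart from ceritinib continued after progression.

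**Inputs for the test.** Phase I n = 246 (section 1.1.2). Phase I grade 3-4 ALT 21%, AST 11%, diarrhea 7% (section 1.3.1.2.1). This trial n = 33 (section 2.3). Assumed: two-sided 0.05, constant monthly event risk h, exponential stopping at rate L, the same risk per month in both trials, no SABR effect.

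**Formula.** The share with an event is p = h/(h + L). An exposure ratio R divides L by R and so multiplies the odds by R: p1 = R·p / (1 − p + R·p). For ALT at R = 2: 0.42/(0.79 + 0.42) = 34.7%.

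**Fisher thresholds.** With control counts fixed at 52, 27 and 17 of 246, the smallest significant excess among 33 patients is 13 (ALT), 8 (AST) and 6 (diarrhea). The chance of reaching it, from Binomial(33, p1), is:

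| Grade 3-4 event | R = 1 | R = 1.25 | R = 1.5 | R = 2 (expected share) |
|---|---|---|---|---|
| ALT | 1.2% | 5% | 12% | 35% (34.7%) |
| AST | 2.4% | 6.5% | 13% | 32% (19.8%) |
| Diarrhea | 2.5% | 6% | 11% | 26% (13.1%) |

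Letting the control count vary as well gives 38%, 28% and 24% at R = 2.

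**Early onset.** If half of the control risk is early and independent of exposure, the R = 2 figures fall to 12-14%; if three quarters is early, to 6-7%.

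**Would a fixed time point repair it?** For ALT, h/L = 0.21/0.79 = 0.266. At the control median, t = ln 2/L, with stopping at L/2 here and no SABR effect, cumulative incidence in this trial is 0.347 × [1 − exp(−(0.266 + 0.5) × 0.693)] = 14.3% (16.8% as 1 − Kaplan-Meier). The control's 21% is a whole-period share, not a value at its median. Setting 14.3% against 21% favours apparent safety: if SABR doubled the monthly risk, the figure would be 26.3%, only slightly above 21%.

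**Patient-time.** Under the same model, events per patient-month have an expected ratio of 1.0 at any R.

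**The case against.** A reader might infer that the control had about half the exposure, so longer treatment will make SABR look toxic. The documents do not support that. They nowhere give Phase I time on treatment. The half comes from setting a historical median PFS against a projection that is the trial's own alternative hypothesis, and without a PFS gain the ratio is near 1.

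Dose may push the other way. Section 1.6 reports the fewest GI events, and none of grade 3 or 4, at 450 mg with food. A rise in grade 3-4 diarrhea from 7% to 13.1% fits poorly with that, and for GI events the net bias could conceal added toxicity. Constant risk is also doubtful: section 7.1.4 lists ALT elevation and diarrhea among first-cycle dose-limiting toxicities, and Table 4-3 reduces dose after toxicity.

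The worked examples are grade 3-4, whereas the planned cuts are none/any and none-mild/moderate-severe. The documents give no control rates for grade 2 or above. For none/any, with the control count varying, R = 2 gives 14% for nausea (82%) and 42% for fatigue (47%), so the size varies widely by event. The baseline is not settled either: grade 3-4 ALT is 21% in section 1.3.1.2.1 and 15.5% in section 7.1.4.

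Finally, sections 2.0 and 9.10.2 also frame safety as description, no decision or stopping rule uses this p-value, and exact intervals and an exposure summary are already planned.

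All of this stands, and it limits the direction, size and consequence of the problem. It does not rescue the test: a second uncontrolled difference makes the p-value harder to interpret.

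**Conclusion.** The point holds as one of confounding without a known sign. Section 9.3 plans a formal test of crude whole-period proportions against a control whose time on drug may differ and whose dose does differ, with no adjustment for either.

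The exposure component alone gives a false excess in about 26-35% of trials at a ratio of 2, 11-13% at 1.5, 5-6.5% at 1.25 and 1-2.5% at 1 for the three grade 3-4 events. This assumes constant monthly risk, no SABR toxicity, 33 vs 246 patients and two-sided 0.05; early onset lowers it. The dose component cannot be sized from the documents and could reverse the net direction.

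The use of the Phase I trial as the safety control is read from section 9.2, since section 9.3 names none. This is a cheap improvement to a stated safety comparison and does not affect the primary analysis.

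**What to change.** In section 9.3:

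1. Delete the Fisher test and its p-value, and name the historical dataset and the rates to be shown.
2. Report whole-period proportions with exact 95% confidence intervals beside the published rates as a descriptive comparison, stating the exposure and dose differences next to them.
3. Add events per patient-month of ceritinib, split before and after first SABR. Match numerator and denominator: all events over full exposure, or first events over time to first event or stopping.
4. Compare these with the control only if its patient-time, or its cumulative incidence at the same time point, is available. Do not set this trial's 7- or 10-month cumulative incidence against the control's whole-period proportion.
5. Align the historical-control wording in the section 9.1 endpoint table.

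The cost is SAP wording and minor programming. Exposure is already summarised under section 9.10, and the treatment-emergent tables already require knowing when events started or worsened. The downside is that the safety comparison has no formal p-value, and the patient-month rates may have no published comparator. Patient-time handles exposure only; the dose difference remains and has to be stated.

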### **9.3.1 Treatment phase and duration of treatment**

Patients eligible for treatment will receive 450 mg daily of ceritinib as part of a 28 day cycle. The first dose of each cycle will be administered after evaluation at the study center. Patients will remain on study and take ceritinib until there is evidence of disease progression by RECIST, unacceptable toxicity, withdrawal of consent, or discontinuation of the trial for any other reason.

If there is oligoprogression amenable to SABR, resumption of ceritinib after SABR will be permitted if the treating oncologist feels the patient would benefit.

### **9.4 Definition of end of the Study**

Cohort A will be completed when 20 patients and cohort B will be completed when 17 patients have evidence of disease progression by RECIST not amenable to SABR requiring discontinuation of ceritinib, unacceptable toxicity, withdrawal of consent, or discontinuation of the trial for any other reason.

At the completion or discontinuation of study medication, all patients will be seen within 30 days for an end of therapy evaluation. This will include a safety assessment for AE's SAE's. Any unused medication will be returned.

### **9.5 Early Termination**

Treatment on protocol may be terminated early if the Principal investigator or institution assess that the safety of the enrolled subjects will be compromised by continuation of the trial. The procedure followed will be that of the premature withdrawal patient and any patients on treatment will be seen as soon as possible.

### **9.6 Data confidentiality**

Information about protocol subjects will be kept confidential and managed under the applicable laws and regulations. Those regulations require a signed subject authorization informing the subject of the following:

- What protected health information (PHI) will be collected from subjects in this protocol
- Who will have access to that information and why
- Who will use or disclose that information
- The rights of a research subject to revoke their authorization for use of their PHI.

In the event that a subject revokes authorization to collect or use PHI, the investigator, by regulation, retains the ability to use all information collected prior to the revocation of subject authorization. For subjects that have revoked authorization to collect or use PHI, attempts should be made to obtain permission to collect follow-up safety information (e.g. has the subject experienced any new or worsened AEs) at the end of their scheduled protocol treatment period.

### **9.7 Statistical methods and data analysis**

### **9.8 Analysis sets**

#### **9.8.1 Full Analysis Set**

The Full Analysis Set (FAS) comprises all enrolled patients.

#### **9.8.2 Safety Set**

The Safety Set includes all patients who received at least one dose of ceritinib medication.

### **9.9 Patient demographics/other baseline characteristics**

Demographic, disease characteristics and other baseline data will be summarized descriptively for the FAS.

### **9.10 Treatments (ceritinib treatment, concomitant therapies, compliance)**

All analyses from this section will be performed on all patients from the safety set. Duration of ceritinib treatment exposure will be summarized.

#### **9.10.1 Handling of missing values/censoring/discontinuations**

All attempts will be made to ensure that the database contains full information for the safety set. No imputation will be applied for missing data.

#### **9.10.2 Safety objectives**

The safety objective is to describe toxicities in patients treated with ceritinib.

##### **9.10.2.1 Analysis set and grouping for the analyses**

For all safety analyses, the safety set will be used. Toxicities will be dichotomized as none versus any adverse event, or none and mild versus moderate to severe adverse event.

The safety summary tables will include assessments from the on-treatment period, unless otherwise specified.

All safety data collected in the study will be listed regardless of the study period with data collected during the pre-treatment and post-treatment period flagged.

##### **9.10.2.2 Adverse events (AEs)**

Summary tables for adverse events (AEs) will include only AEs that started or worsened during the on-treatment period, the treatment-emergent AEs. However, all safety data (including those from the pre and post-treatment periods) will be listed and those collected during the pre-treatment and post-treatment period are to be flagged.

The incidence of treatment-emergent adverse events (new or worsening from baseline) will be summarized by system organ class and or preferred term, severity (based on CTCAE grades), type of adverse event, relation to study treatment by

Deaths reportable as SAEs and non-fatal serious adverse events will be listed by patient and tabulated by type of adverse event and.

Specific safety event categories (SEC) will be considered. Such categories consist of one or more well-defined safety events which are similar in nature and for which there is a specific clinical interest in connection with the study treatment(s).

For each specified category, number and percentage of patients with at least one event per category will be summarized.

##### **9.10.2.3 Other safety data**

Other safety data (including ECGs, vital signs and weight) will be summarized and listed, notable values will be flagged, and any other information collected will be listed as appropriate.

## **10.0 Ethical considerations and administrative procedures**

### **10.1 Regulatory and ethical compliance**

This clinical study was designed, shall be implemented and reported in accordance with the ICH Harmonized Tripartite Guidelines for Good Clinical Practice, with applicable local regulations (including European Directive 2001/20/EC and US Code of Federal Regulations Title 21), and with the ethical principles laid down in the Declaration of Helsinki.

### **10.2 Informed consent procedures**

Eligible patients will only be included on this after providing written IRB/IEC/REB-approved informed consent.

Informed consent must be obtained before conducting any protocol-specific procedures (i.e. all of the procedures described in the protocol). The process of obtaining informed consent should be documented in the patient source documents. The date when a subject's Informed Consent was actually obtained will be captured in the clinical trial record. The informed consent document will be approved by the IRB.

### **10.3 Discontinuation of the study**

This study will discontinue if terminated by the Institutional Review Board or at the discretion of the Principal Investigator.

### **10.4 Publication of the study and results**

The results of this study will be updated and posted per regulatory requirements, including (but not limited) to databases such as [clinicaltrials.gov](http://clinicaltrials.gov).

#### **10.4.1 Communication and Publication of Clinical Trial Results**

All submitted manuscripts will comply with institutional guidelines and with authorship guidelines of the International Committee of Medical Journal Editors.

### **10.5 Study documentation, record keeping and retention of documents**

The investigator/institution should maintain the trial documents as specified in Essential Documents for the Conduct of a Clinical Trial (ICH E6 Section 8) and as required by applicable regulations and/or guidelines. The investigator/institution should take measures to prevent accidental or premature destruction of these documents.

### **10.6 Confidentiality of study documents and patient records**

The investigator must ensure anonymity of the patients; patients must not be identified by names in any trial documents. Signed informed consent forms and patient enrollment log must be kept strictly confidential to enable patient identification.

### **10.7 Audits and inspections**

Source data/documents must be available to inspections by Health Authorities.

## **11.0 STUDY MANAGEMENT**

### **11.1 Conflict of Interest**

Any investigator who has a conflict of interest with this study (patent ownership, royalties, or financial gain greater than the minimum allowable by their institution, etc.) must have the conflict reviewed by the UTSW COI Committee and IRB according to UTSW Policy on Conflicts of Interest. All investigators will follow the University conflict of interest policy.

